2.4 Determination of sample size

No formal statistical sample size calculation has been performed for the dose escalation modules in study ONC001.

The number of participants likely to be enrolled in Part B depends on how many dose levels are needed to define the RP2D-T for combination therapy. In Part B, up to 27 eligible participants will be enrolled. It is expected that up to 3 dose levels of UCB6114 will be explored in combination with the TFD/TPI dosing regimen, respectively. However, additional dose levels may be added based on emerging data and recommendations of the SMC.

Between 3 and 9 participants are expected to be enrolled at each dose level of UCB6114 depending on the observed toxicity/observation of DLTs. An administrative decision to stop enrolling into Part B may be made by the Sponsor at any time. “Dose level” refers to a particular UCB6114 dose, that can be given to one or more cohorts, not necessarily consecutively.

The operating characteristics of the mTPI design were evaluated using a simulation approach under four scenarios (see Table 2-1) and based on no DLTs observed in the first 2 cohorts in Part A monotherapy treatment (UCB6114 100mg and 250mg). The results of this evaluation can be seen in Table 2-2.

Table 2-1: Scenarios used for evaluating the operating characteristics of the mTPI design. Orange cells indicate the correct decision assuming a maximum tolerated toxicity of 25% (equivalence limits 20%, 30%)

UCB6114 Dose	Probability of a DLT			
	Scenario 1	Scenario 2	Scenario 3	Scenario 4
Dose 1 (500 mg)	0.05	0.05	0.15	0.25
Dose 2 (1000 mg)	0.05	0.15	0.25	0.35
Dose 3 (2000 mg)	0.05	0.25	0.35	0.50

Table 2–2: Evaluation of the operating characteristics of the mTPI design with a target maximum tolerated toxicity of 25%, using 5000 simulated trials for each scenario. Orange cells indicate the correct decision.

Final UCB6114 Dose Selected	Scenario 1	Scenario 2	Scenario 3	Scenario 4
	% of Simulations (Number of Simulations)			
Dose 1 (500 mg)	3.9% (196)	5.2% (262)	31.6% (1580)	53.3% (2666)
Dose 2 (1000 mg)	3.9% (195)	35.1% (1755)	40% (1999)	26.7% (1337)
Dose 3 (2000 mg)	91.4% (4571)	58.9% (2947)	21.6% (1080)	3.8% (191)
Overly Toxic at First Cohort	0.8% (38)	0.7% (36)	6.7% (336)	15.2% (758)
Overly Toxic after First Cohort	0	0	0.1% (5)	1% (48)

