8.3 Clinical laboratory evaluations

The use of multiple local laboratories (1 per site in the UK and US) in Part B of this study has meant that results have been recorded in different units and with reference to different normal ranges, and further, for some laboratory tests, different normal ranges have been applied to males and females and age groups. As a first step to ensure comparability of laboratory results, results and normal ranges will be converted to the same International System of Units (SI) units using UCB’s standard conversion factors. This will be programmed at the Study Data Tabulation Model (SDTM) level. Note though that the simple conversion to SI units does not represent a full homogenization of results from different local laboratories using different methods. To ensure full comparability, the observed laboratory results will be normalized to a unique set of standard reference ranges using the location-scale normalization formula (Chuang-Stein, 1992) which normalizes all results in relation to a standard set of reference ranges (for hematology, clinical chemistry and coagulation parameters):

$$s = L_S + (x - L_X) \frac{(U_S - L_S)}{(U_X - L_X)}$$

and when the standard lower limit is 0: $s = x \frac{U_S}{U_X}$ where:

s = normalized observed value

x = original observed value in SI units

L_S = Lower Limit of the reference range chosen to be the standard reference range

U_S = Upper Limit of the reference range chosen to be the standard reference range

L_X = Lower Limit of the reference range associated with the original observed value in SI units (local laboratory reference range)

U_X = Upper Limit of the reference range associated with the original observed value in SI units (local laboratory reference range)

This transformation preserves the distance of the original laboratory result from the lower limit of normal as a multiple of the specified standard reference range.

Note that the choice of the standard reference range is arbitrary, however, the most recent reference ranges used by ICON Central Laboratories (including the age and gender specific reference ranges for parameters, where available) will be used to normalize the results in this study.

Normalization of the laboratory results will be performed in the ADaM programming by ICON.

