All normalized laboratory data (hematology, serum chemistry and coagulation) and changes from Baseline for numeric variables will be listed for participants who have at least one value outside of the reference range. All urinalysis data will be listed for all participants. Data will be listed by study participant, laboratory panel, laboratory parameter and visit within each treatment group. Any laboratory measurements that are BLQ or ALQ will be handled as described in [Section 4.2.2](#). For the relevant numeric laboratory parameters, the reference ranges supplied by the local analytical laboratory will be used to flag values outside the reference range as low or high in this listing. For the parameters for which the local laboratory cannot supply the reference ranges, the reference ranges provided by ICON Central Laboratories will be used instead. A listing of all laboratory results outside of the reference range will also be presented. The reference ranges will also be reported in the listings.

In addition, for the relevant hematology, clinical chemistry and coagulation laboratory tests, CTCAE severity grades (Grade 1, Grade 2, Grade 3, Grade 4) will be applied (where possible) in the ADaM programming according to NCI CTCAE Version 5.0, and these grades will also be listed for the relevant laboratory parameters. Note that Grade 0 will be applied in cases where a result is normal for the relevant laboratory test and Grade 5 is not applicable in the grading of laboratory data.

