Observed normalized values and changes from Baseline in the hematology, serum chemistry and coagulation parameters presented below in [Table 8-1](#) will be summarized at each visit. In addition, for each of these parameters, the Baseline value, the minimum, maximum, average and last post-Baseline value for each participant will be summarized by cycle using descriptive statistics. These post-Baseline summary measures will be calculated based on all available scheduled postdose values within each cycle, i.e. from Day 8 of the current cycle up to Day 1 (pre-UCB6114) of the subsequent cycle. The last value in a cycle will be the predose value of the subsequent cycle where a subsequent cycle occurs, otherwise it will be the value at the last scheduled assessment. If only one value is available then the average will not be calculated and presented but this value will be used for the minimum, maximum and last post-Baseline summary measures. These summary measures for each cycle will also be listed.

The summaries of normalized hematology, serum chemistry and coagulation values and changes from Baseline will also be presented by Gastric/GEJ-Cancer and CRC tumor type depending on the number of participants with specific tumor types.

For those laboratory parameters with a CTCAE toxicity assigned, shift tables for the change from Baseline in CTCAE severity grade at each visit and to the worst post-Baseline CTCAE severity grade during the Treatment Period will be presented.

Table 8-1: Clinical Laboratory Assessments

Laboratory Assessment	Laboratory Parameters
Hematology	Platelet Count, RBC Count, Hemoglobin, Hematocrit, RBC Indices (MCV, MCH, MCHC), WBC Count with Differential (Absolute Neutrophils, Absolute Lymphocytes, Absolute Monocytes, Absolute Eosinophils, Absolute Basophils)
Clinical Chemistry	ALT, AST, ALP ^a , Bicarbonate, Sodium, Potassium, Magnesium, Chloride, Calcium, Total Bilirubin, BUN or Urea, Serum Creatinine, Glucose (non-fasted), Phosphorus or Phosphate, Albumin, Total Protein, Uric Acid, Amylase, GGT, Cholesterol, Creatine Kinase, CRP, LDH, Lipase, Triglycerides
Coagulation	aPTT and either prothrombin time or INR
Routine Urinalysis	Specific Gravity, pH, Glucose, Protein, Blood, Ketones, Bilirubin, Urobilinogen, Nitrite, Leukocyte Esterase by Dipstick Microscopic Examination (if blood or protein is abnormal, including crystals)

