8.3 Clinical laboratory evaluations

The use of multiple local laboratories (1 per site in the UK and US) in Part C of this study has meant that results have been recorded in different units and with reference to different normal ranges, and further, for some laboratory tests, different normal ranges have been applied to males

and females and age groups. As a first step to ensure comparability of laboratory results, results and normal ranges will be converted to the same International System of Units (SI) units using UCB's standard conversion factors. This will be programmed at the Study Data Tabulation Model (SDTM) level. Note though that the simple conversion to SI units does not represent a full homogenization of results from different local laboratories using different methods. To ensure full comparability, the observed laboratory results will be normalized to a unique set of standard reference ranges using the location-scale normalization formula (Chuang-Stein, 1992) which normalizes all results in relation to a standard set of reference ranges (for hematology, clinical chemistry and coagulation parameters):

$$s = L_S + (x - L_X) \frac{(U_S - L_S)}{(U_X - L_X)}$$

and when the standard lower limit is 0: $s = x \frac{U_S}{U_X}$ where:

s = normalized observed value

x = original observed value in SI units

L_S = Lower Limit of the reference range chosen to be the standard reference range

U_S = Upper Limit of the reference range chosen to be the standard reference range

L_X = Lower Limit of the reference range associated with the original observed value in SI units (local laboratory reference range)

U_X = Upper Limit of the reference range associated with the original observed value in SI units (local laboratory reference range)

This transformation preserves the distance of the original laboratory result from the lower limit of normal as a multiple of the specified standard reference range.

Note that the choice of the standard reference range is arbitrary, however, the most recent reference ranges used by ICON Central Laboratories (including the age and gender specific reference ranges for parameters, where available) will be used to normalize the results in this study.

Normalization of the laboratory results will be performed in the ADaM programming by ICON.

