All laboratory data (hematology, serum chemistry and coagulation) and changes from Baseline for numeric variables will be listed for participants who have at least one value outside of the reference range. All urinalysis data will be listed for all participants. Data will be listed by study participant, laboratory panel, laboratory parameter and visit within each treatment group. Any laboratory measurements that are BLQ or ALQ will be handled as described in [Section 4.2.2](#).

For the relevant numeric laboratory parameters, the reference ranges supplied by the local analytical laboratory will be used to flag values outside the reference range as low or high in this listing. For the parameters for which the local laboratory cannot supply the reference ranges, the reference ranges provided by ICON Central Laboratories will be used instead. A listing of all laboratory results outside of the reference range will also be presented. The reference ranges will also be reported in the listings.

In addition, for the relevant hematology, clinical chemistry and coagulation laboratory tests, CTCAE severity grades (Grade 1, Grade 2, Grade 3, Grade 4) will be applied (where possible) in

the ADaM programming according to NCI CTCAE Version 5.0, and these grades will also be listed for the relevant laboratory parameters. Note that Grade 0 will be applied in cases where a result is normal for the relevant laboratory test and Grade 5 is not applicable in the grading of laboratory data.

Observed values and changes from Baseline in the hematology, serum chemistry and coagulation parameters presented below in [Table 8-1](#) will be summarized at each visit. In addition, for each of these parameters, the Baseline value, the minimum, maximum, average and last post-Baseline value for each participant will be summarized by cycle using descriptive statistics. These post-Baseline summary measures will be calculated based on all available scheduled postdose values within each cycle, i.e. from Day 8 of the current cycle up to Day 1 (pre-UCB6114) of the subsequent cycle. The last value in a cycle will be the predose value of the subsequent cycle where a subsequent cycle occurs, otherwise it will be the value at the last scheduled assessment. If only one value is available then the average will not be calculated and presented but this value will be used for the minimum, maximum and last post-Baseline summary measures. These summary measures for each cycle will also be listed.

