The summaries of normalized hematology, serum chemistry and coagulation values and changes from Baseline will also be presented by Gastric/GEJ-Cancer and CRC tumor type depending on the number of participants with specific tumor types.

For those laboratory parameters with a CTCAE toxicity assigned, shift tables for the change from Baseline in CTCAE severity grade at each visit and to the worst post-Baseline CTCAE severity grade during the Treatment Period will be presented.

Table 8-1: Clinical Laboratory Assessments

Laboratory Assessment	Laboratory Parameters
Hematology	Platelet Count, RBC Count, Hemoglobin, Hematocrit, RBC Indices (MCV, MCH, MCHC), WBC Count with Differential (Absolute Neutrophils, Absolute Lymphocytes, Absolute Monocytes, Absolute Eosinophils, Absolute Basophils)
Clinical Chemistry	ALT, AST, ALP ^a , Bicarbonate, Sodium, Potassium, Magnesium, Chloride, Calcium, Total Bilirubin, BUN or Urea, Serum Creatinine, Glucose (non-fasted), Phosphorus or Phosphate, Albumin, Total Protein, Uric Acid, Amylase, GGT, Cholesterol, Creatine Kinase, CRP, LDH, Lipase, Triglycerides
Coagulation	aPTT and either prothrombin time or INR
Routine Urinalysis	Specific Gravity, pH, Glucose, Protein, Blood, Ketones, Bilirubin, Urobilinogen, Nitrite, Leukocyte Esterase by Dipstick Microscopic Examination (if blood or protein is abnormal, including crystals)
Screening Tests	Pregnancy tests: FSH and estradiol (for women of non-childbearing potential only); serum or urine hCG pregnancy test (for women of childbearing potential) Bone turnover markers: blood BAP, blood CTx, urinary NTx and urinary CTxII Tumor markers: e.g. PSA, CA125, CA19-9

ALP=alkaline phosphatase; ALT=alanine aminotransferase; aPTT=activated partial thromboplastin time; AST=aspartate aminotransferase; BAP=bone alkaline phosphatase; BUN=blood urea nitrogen; CA=cancer antigen; CRP=C-reactive protein; CTx=C-terminal telopeptide; FSH=follicle-stimulating hormone; GGT=gamma glutamyl transferase; hCG=human chorionic gonadotropin; INR=international normalized ratio; LDH=lactate dehydrogenase; MCH=mean corpuscular hemoglobin; MCHC=mean corpuscular hemoglobin concentration; MCV=mean corpuscular volume; NTx=N-terminal telopeptide; PSA=prostate specific antigen; RBC=red blood cell; WBC=white blood cell.

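### Part B flags a listing of normalized laboratory values with un-normalized local ranges, the scale for CTCAE grades and ×ULN criteria is unstated, and Part C is inconsistent about normalization

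*SAP*

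**What the plan says.** Section 8.3 of both SAPs starts from the same premise. Each site uses its own laboratory, results and ranges are converted to SI units at SDTM level, and the plan accepts that "the simple conversion to SI units does not represent a full homogenization of results from different local laboratories using different methods". It therefore continues: "To ensure full comparability, the observed laboratory results will be normalized to a unique set of standard reference ranges". The target ranges are the central laboratory's most recent ones, and normalization is done in the ADaM programming.

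**Part B.** The listing is defined by "All normalized laboratory data (hematology, serum chemistry and coagulation) and changes from Baseline for numeric variables will be listed", restricted to participants with at least one value outside the reference range. For flagging within that listing, "the reference ranges supplied by the local analytical laboratory will be used to flag values outside the reference range as low or high"; central ranges are substituted only where a local laboratory cannot supply one. The ranges are also printed in the listings. The by-visit table covers "Observed normalized values and changes from Baseline in the hematology, serum chemistry and coagulation parameters".

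**Grades and liver criteria, both parts.** CTCAE laboratory grades are also derived in ADaM. The liver-function and PDILI criteria are written as multiples of ULN. Neither is tied to the SI result or to the normalized one.

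**Part C.** The normalization rule is the same, but the listing sentence does not contain the word normalized, and the by-visit table covers "Observed values and changes from Baseline in the hematology, serum chemistry and coagulation parameters". The tumor-type paragraph then says: "The summaries of normalized hematology, serum chemistry and coagulation values and changes from Baseline will also be presented".

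**The concern.** A normalized value can be judged only against the range it was normalized to. Part B, as worded, places values on the central scale beside a low/high rule on the local scale. The flag would then depend partly on how the site's range differs from the central one, and not only on the participant.

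The flags appear in the laboratory listing, and the same undefined range decides who enters it and which results enter the separate listing of out-of-range values. Grades feed the shift tables. The ×ULN thresholds feed the liver-function and PDILI summaries, and section 8.2.1 uses ×ULN thresholds to define the Hy's Law AESI. Section 2.4 expects 3 to 9 participants per dose level, so one reclassified participant would be visible.

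In Part C the question is whether the main table is on the harmonized scale at all. If raw values were used, dose-level summaries would pool laboratories that section 8.3 itself says are not comparable.

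**Working it through.** The plan states no figure to reproduce and no numeric reference ranges. The formula is the plan's; every range below is an assumption.

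**1. Formula (section 8.3).** With local range `LX–UX` and standard range `LS–US`, `s = LS + (x − LX)·R`, where `R = (US − LS)/(UX − LX)`. When `LS = 0`, the plan uses `s = x·US/UX`.

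**2. Matched scales.** From the first form, `s − LS = (x − LX)·R` and `s − US = (x − UX)·R`, with `R > 0`. Raw against local and normalized against standard therefore give the same flag; a random check agreed in 200,000 of 200,000 cases. With `LS = 0`, high flags again agreed in all 200,000, but low/normal flags differed in 35,252 (local lower limits drawn above 0), because no positive value can fall below a lower limit of 0. Raw against local is thus the pairing that always keeps the laboratory's own low flag.

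**3. Mixed scales (the literal Part B wording).**

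| Local | Standard | Raw x | Status on local range | s | s against local range |
|---|---|---|---|---|---|
| 5–55 | 10–40 | 60 | high | 10 + 55×30/50 = 43 | not flagged |
| 10–40 | 5–55 | 39 | normal | 5 + 29×50/30 = 53.3 | high |
| 130–170 | 120–160 | 132 | normal | 120 + 2×40/40 = 122 | low |
| 130–170 | 120–160 | 172 | high | 120 + 42×40/40 = 162 | not flagged |

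**4. Share misflagged.** Assume the local range covers the central 95% of a normal distribution (width 3.92 SD) and the standard range has the same width but lies lower by a fraction d of it. False lows are `Φ(−1.96 + 3.92d) − 0.025`; missed highs are `Φ(1.96 + 3.92d) − 0.975`.

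| d | False low | Missed high | Total |
|---|---|---|---|
| 5% | 1.39% | 0.95% | 2.3% |
| 10% | 3.34% | 1.57% | 4.9% |
| 25% | 13.85% | 2.34% | 16.2% |

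If flags are set on the raw values, none is wrong.

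**5. Multiples of ULN.** Put `x = k·UX` in the first form: `s/US = 1 + (k − 1)·(1 − LS/US)/(1 − LX/UX)`. With `LS > 0` the multiple is kept only if the two ranges have the same ratio of lower to upper limit.

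- Local 5–55, standard 10–40, x = 165 (k = 3): 1 + 2×0.75/0.9091 = 2.65, so s = 106 and ≥3×ULN is missed.
- Local 10–50, standard 5–40, x = 150 (k = 3): 1 + 2×0.875/0.8 = 3.19, so s = 127.5.
- Local ULN 55, standard 0–40, x = 165: s = 165×40/55 = 120 = 3.00×ULN. This branch preserves multiples.

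The first form can also go negative: neutrophils 0.2, local 2.0–7.5, standard 1.5–8.0, give 1.5 − 1.8×6.5/5.5 = −0.63. That would affect a grade only if grades were taken from s.

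**6. Parts B and C side by side.**

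| Output | Part B | Part C |
|---|---|---|
| Normalization required | yes | yes |
| Listing | normalized | word absent |
| Low/high flag in listing | local range | local range |
| Main by-visit table | normalized | word absent |
| Tumor-type table | normalized | normalized |

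**The case against.** The strongest reply is that Part B names the range used for flagging but never says that the normalized number is what is compared. The fallback supports this. Where no local range exists, the formula cannot be applied, so the central-range fallback must concern an un-normalized result; and if flags were set on normalized values, the central range would be the rule rather than the fallback. Flagging the SI result with its own range and carrying the flag across gives correct flags. This stands as a plausible intention, so a reader may not conclude that the flags will certainly be wrong. It does not rescue the listing as specified. The flag source is still unstated, and a local range printed beside a normalized value would mislead: in the first example, 43 would be marked high next to 5–55.

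Three other stronger readings are tempting and not supported:

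- **Part C's main table pools raw values.** Section 8.3 itself calls s a normalized observed value, so observed need not mean raw, and the word also in the tumor-type sentence implies a normalized main table. An omitted word is the likelier explanation. The text is contradictory, not a settled raw-value plan.
- **Between-site comparisons are wrong.** Sections 3.7 and 4.6 of both SAPs plan no laboratory summaries by site. Any harm would lie in pooled dose-level summaries.
- **Grades and ×ULN criteria use normalized values.** The plan does not say so. Sharing the ADaM environment with normalization is not evidence of it, and the zero-lower-limit form keeps ULN multiples exactly. What holds is that the scale is unstated and, for other parameters, matters.

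**Conclusion.** The point holds as a defect of specification, with one rule that misflags if programmed as written. Part B's listing pairs normalized values with un-normalized local ranges: taken literally, flags are wrong wherever the ranges differ enough to move a value across a limit; taken charitably, the flags are right but a printed local range does not fit the value shown. The scale for CTCAE grades and ×ULN/PDILI criteria needs stating, because normalization generally changes ULN multiples when the standard lower limit is above 0. Part C contradicts itself and differs from Part B.

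The size cannot be fixed from the document. The 2.3% to 16.2% rests on an assumed normal distribution, equal widths and shifts of 5% to 25%; it is zero if raw values are flagged.

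This should be corrected, but it does not threaten the primary endpoints. Laboratory data are other safety endpoints in section 2.2.1.2, and AE grades and DLTs are recorded by the investigator, so TEAE and DLT incidence do not depend on these flags.

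**What to change.** In section 8.3 of both SAPs:

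1. State that low/high flags, selection for the abnormal-value listings, CTCAE grades and all ×ULN and PDILI criteria are derived from the SI result with that result's own local range, using the central range only where no local range exists.
2. Print beside each value the range that matches it: local beside the SI result, standard beside the normalized result.
3. Reserve normalized values for descriptive summaries and change from Baseline.
4. In Part C, make the by-visit sentence read as Part B's does, "Observed normalized values and changes from Baseline in the hematology, serum chemistry and coagulation parameters", so that the main and tumor-type tables, and the two parts, share one scale. State in Part C's listing paragraph which values are shown. Adding only the word normalized there would import Part B's mismatch.

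The cost is SAP wording and an ADaM specification update; the SI results and ranges are already in SDTM. The small downside is that listings carry both the SI and the normalized value.

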8.2.1 Adverse events of special interest

An AESI is any AE that a regulatory authority has mandated be reported on an expedited basis, regardless of the seriousness, expectedness, or relatedness of the AE to the administration of a UCB product/compound.

For ONC001, potential Hy's Law is used to identify AESIs and is defined using the laboratory data and the following potential drug-induced liver injury (PDILI) criteria:

- $\geq 3x$ upper limit of normal (ULN) alanine aminotransferase (ALT) *or* aspartate aminotransferase (AST) with coexisting $\geq 2x$ ULN total bilirubin in the absence of $\geq 2x$ ULN alkaline phosphatase (ALP), with no alternative explanation for the biochemical abnormality;
- Study participants who have evidence of liver metastases may be considered to have an alternate etiology for the described laboratory abnormalities.

All AESIs will be flagged on the listing of AEs.

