Screening Tests	Pregnancy tests: FSH and estradiol (for women of non-childbearing potential only); serum or urine hCG pregnancy test (for women of childbearing potential) Bone turnover markers: blood BAP, blood CTx, urinary NTx and urinary CTxII Tumor markers: e.g. PSA, CA125, CA19-9

ALP=alkaline phosphatase; ALT=alanine aminotransferase; aPTT=activated partial thromboplastin time; AST=aspartate aminotransferase; BAP=bone alkaline phosphatase; BUN=blood urea nitrogen; CA=cancer antigen; CRP=C-reactive protein; CTx=C-terminal telopeptide; FSH=follicle-stimulating hormone; GGT=gamma glutamyl transferase; hCG=human chorionic gonadotropin; INR=international normalized ratio; LDH=lactate dehydrogenase; MCH=mean corpuscular hemoglobin; MCHC=mean corpuscular hemoglobin concentration; MCV=mean corpuscular volume; NTx=N-terminal telopeptide; PSA=prostate specific antigen; RBC=red blood cell; WBC=white blood cell.

a including liver-specific ALP for use in assessing participants with bone metastases at Screening. In the case of bone metastases liver function abnormalities considered potential Hy's law cases, the liver-specific ALP must be separated from the total in participants with bone metastases and used to assess the liver function instead of the total ALP

The screening laboratory tests included above in [Table 8-1](#) will be listed only.

Liver function abnormalities will be defined using the following criteria:

- ALT or AST $\geq 2 \times \text{ULN}$
- ALT or AST $\geq 3 \times \text{ULN}$
- Total bilirubin $\geq 2 \times \text{ULN}$
- Total bilirubin $\geq 3 \times \text{ULN}$

- ALT or AST $\geq 5\times$ ULN
- ALT or AST $\geq 8\times$ ULN
- ALT or AST $\geq 3\times$ ULN AND total bilirubin $\geq 2\times$ ULN ($>35\%$ direct bilirubin)

For the subgroups of participants with liver metastases and without liver metastases at Baseline, the number and percentage of participants in each liver function abnormality category will be summarized at each visit.

In addition, participants with PDILI criteria are those that fulfill the following laboratory data (based on liver function tests) criteria at a visit:

- AST or ALT and total bilirubin within the normal range at Baseline and AST or ALT $\geq 3\times$ ULN concurrent with total bilirubin $\geq 2\times$ ULN;

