- AST, ALT or total bilirubin above ULN at Baseline and AST or ALT ≥ 2 times Baseline values AND AST or ALT $\geq 3\times$ ULN (participants without liver metastases at Baseline)/AST or ALT $\geq 8\times$ ULN (participants with liver metastases at Baseline) concurrent with total bilirubin above ULN at Baseline and total bilirubin ≥ 2 times Baseline value or $\geq 3\times$ ULN (whichever is lower).

All relevant laboratory data collected for participants with a PDILI event (i.e. liver function tests) will be listed at the visits at which at least one of the above criteria was fulfilled.

The number and percentage of participants meeting different combinations of the ALT, AST and total bilirubin criteria defined above will be summarized by treatment group. This summary will be presented for all participants as well as for the subgroups of participants who had liver metastases at Baseline and participants without liver metastases at Baseline.

A separate listing will also be produced containing drug-induced liver injury -relevant family medical history, lifestyle data (alcohol consumption or drug abuse in the previous 6 months), hepatic event supplemental medical history and any hepato-toxic medications taken for participants in the SS with a PDILI event.

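### The second PDILI criterion in SAP Section 8.3 contradicts itself, so a participant with both AST and ALT raised and bilirubin normal at Baseline can meet neither PDILI criterion

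*SAP*

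**What the plan says.** Section 8.3 of the Part B plan defines PDILI participants by laboratory criteria applied at a visit. Part C repeats the wording.

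- **Criterion 1** applies when the participant has "AST or ALT and total bilirubin within the normal range at Baseline and AST or ALT" later reaches at least 3x ULN, with concurrent bilirubin of at least 2x ULN.
- **Criterion 2** opens with "AST, ALT or total bilirubin above ULN at Baseline and AST or ALT". It asks for a transaminase of at least twice its Baseline value and at least 3x ULN (8x ULN if liver metastases were present at Baseline), and then "concurrent with total bilirubin above ULN at Baseline and total bilirubin" reaching the lower of twice its Baseline value and 3x ULN.

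Two outputs depend on these criteria. Liver test data for participants with a PDILI event "will be listed at the visits at which at least one of the above criteria was fulfilled". A second listing holds family history, lifestyle data, "hepatic event supplemental medical history and any hepato-toxic medications taken for participants in the SS with a PDILI event".

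**The concern.** The opening of criterion 2 lets a participant in on any one of three raised Baseline values. The bilirubin limb then makes one of those three compulsory. The two clauses cannot both be meant: if raised Baseline bilirubin is always required, the choice of three at the start has no effect.

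The result is not ordered by Baseline liver status. Participants with everything normal at entry can be flagged, and so can those with transaminases and bilirubin all raised. The group between them, with both transaminases raised and bilirubin normal, cannot.

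At stake are the PDILI label and the two listings built on it. For this group, those outputs would be empty because of the wording rather than because no event occurred.

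**Working it through.** The SAP states no figure to reproduce, so the check is on the logic.

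**Inputs** (all from Section 8.3). Let a0, l0 and b0 be Baseline AST, ALT and total bilirubin as multiples of ULN, and a, l and b the values at a later visit. Let k = 3 without liver metastases at Baseline and k = 8 with them. Normal is taken as at or below 1.

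- C1 = (a0 ≤ 1 or l0 ≤ 1) and b0 ≤ 1 and (a ≥ 3 or l ≥ 3) and b ≥ 2
- C2 = (a0 > 1 or l0 > 1 or b0 > 1) and [(a ≥ 2·a0 and a ≥ k) or (l ≥ 2·l0 and l ≥ k)] and b0 > 1 and b ≥ min(2·b0, 3)

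**Step 1: the entry clause.** Whenever b0 > 1 holds, the entry clause of C2 holds automatically. Since C2 always requires b0 > 1, the entry clause neither admits nor excludes anyone.

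**Step 2: every Baseline state.**

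| AST and ALT at Baseline | Bilirubin at Baseline | C1 can be met | C2 can be met |
|---|---|---|---|
| both normal | normal | yes | no |
| exactly one raised | normal | yes, on the literal *or* | no |
| both raised | normal | **no** | **no** |
| any | raised | no | yes |

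**Step 3: an example.** Baseline (2, 2, 0.8) rises to (20, 20, 10). C1 fails because neither transaminase was normal at Baseline. C2 fails because b0 = 0.8. The later values never enter the decision.

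**Step 4: enumeration.** The grid had 9 Baseline values per test (0.5x to 5x ULN, 6 of them above ULN) and 11 later values per test (0.5x to 40x ULN).

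- Both transaminases raised, bilirubin normal: 6 × 6 × 3 = 108 Baseline states; 108 × 11³ = 108 × 1,331 = 143,748 combinations.
- Of these, ALT or AST ≥ 3x ULN with bilirubin ≥ 2x ULN: (11² − 4²) × 8 = 840 per Baseline state; 108 × 840 = 90,720.
- Meeting C1 or C2: 0 of 143,748, with or without liver metastases.
- Comparison group, exactly one transaminase raised and bilirubin normal: 2 × 6 × 3 × 3 = 108 Baseline states, again 90,720 combinations at those levels. C1 catches all 90,720.

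These are counts of grid points that test the rule. They are not frequencies of patients.

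**Step 5: the wording of criterion 1.** The second row of the table depends on reading *or* literally. If a programmer reads criterion 1 as requiring both transaminases to be normal, participants with only one raised and normal bilirubin also fall outside both criteria, and the gap widens.

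**The case against.** **The bilirubin limb might be grouped differently.** One could read it as (raised at Baseline and at least doubled) or (at least 3x ULN). On the same grid that would flag 68,607 combinations without metastases and 52,647 with them. It does not fit the text: the limb takes the lower of twice Baseline and 3x ULN, which makes them one threshold and leaves the Baseline condition standing over both.

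**Other outputs still show the abnormality.** This objection stands, and it limits the point. A reader might infer that such a participant goes unseen in the liver-safety output altogether. The SAP does not support that:

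- The Hy's Law rule in Section 8.2.1 "is used to identify AESIs and is defined using the laboratory data" and carries no Baseline condition. It has an ALP condition, needs the absence of another explanation, and says "Study participants who have evidence of liver metastases may be considered to have an alternate etiology for the described laboratory abnormalities", which permits exclusion but does not require it.
- For the liver function categories, "the number and percentage of participants in each liver function abnormality category will be summarized at each visit". Six of the seven use a single threshold with no Baseline or direct-bilirubin condition, and the example in Step 3 meets all six. The combined category needs a direct bilirubin fraction, while the chemistry row of Table 8-1 names only total bilirubin.
- Section 8.3 also summarizes combinations of the ALT, AST and bilirubin criteria, lists laboratory data for anyone with a value out of range, and gives CTCAE shift tables. Sections 6.5 and 6.6 list medical history and medications generally.

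None of these restores the PDILI label or triggers the supplemental hepatic listing.

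**The size is easily overstated.** A reader might assume that 20% to 40% of up to 27 participants per part enter in this state (0.20 × 27 = 5.4; 0.40 × 27 = 10.8) and call 5 to 11 participants missed. The SAP gives no such prevalence. That figure would also count a Baseline group, not missed events: a miss also needs an on-study rise in transaminases and bilirubin. Nor does the SAP say that criterion 2 was written for this group in particular. It only splits the transaminase threshold by liver metastases.

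**No decision rests on the flag.** The primary endpoints are TEAEs and DLTs, escalation uses the DLT Evaluable Set, and the SAP ties neither to PDILI. This stands and lowers the severity.

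**Conclusion.** The contradiction is real and present in both parts. On the plain text, a participant with both AST and ALT above ULN and normal bilirubin at Baseline cannot be a PDILI case under Section 8.3 at any later value. This follows from the wording alone and needs no assumption about prevalence.

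The consequence is confined to the PDILI flag, the PDILI laboratory listing and the supplemental hepatic listing. A participant could qualify as a Hy's Law AESI under Section 8.2.1 and still be missing from both listings. How many participants or events this would affect cannot be derived from the SAP. The point should be fixed before the listings are programmed, but it does not threaten the primary endpoints or the escalation decisions.

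**What to change.** In Section 8.3 of both plans, reconcile the entry clause and the Baseline bilirubin clause of criterion 2 with each other and with the protocol's PDILI text. Participants admitted only by raised AST or ALT then need a bilirubin condition that they can meet. The sponsor sets the threshold.

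Clarify AST or ALT in criterion 1 at the same time, so that every Baseline state is covered. Simply requiring both transaminases to be normal would lose cases now flagged. Take a participant with liver metastases, Baseline ALT and bilirubin normal and AST 1.3x ULN, who later reaches ALT 5x and bilirubin 3x ULN with AST below 8x. Criterion 1 flags this as now written. Moved to criterion 2, the participant would face the 8x ULN limb and drop out. Any such loss should be an explicit, recorded decision.

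The cost is a short text change to the PDILI criteria in each plan and one revised derivation, and possibly a few more participants listed for review. A table of Baseline states like the one in the working would serve as the programming check.
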